Primary Efficacy Objective: Evaluate the efficacy of treatment at Day 28 following high-titer Anti- SARS-CoV-2 plasma versus control (SARS-CoV-2 non-immune plasma) in subjects exposed to COVID-19 at day 28.

Primary Endpoint: Cumulative incidence of development of COVID-19 disease (symptoms compatible with infection and/or + molecular testing) regardless of disease severity.

Primary Safety Objective: Evaluate the safety of treatment with high-titer Anti- SARS-CoV-2 plasma versus control (SARS-CoV-2 non-immune plasma) in subjects exposed to COVID-19

Primary Safety Endpoints:

1. Cumulative incidence of serious adverse events categorized separately as either severe infusion reactions and ARDS during the study period
2. Cumulative incidence of grade 3 and 4 adverse events during the study period

Secondary Objectives:

1. Cumulative incidence of disease severity between the anti-SARS-CoV-2 convalescent plasma and control groups after individuals develop SARS-CoV-2 infection. Severity of disease will be measured using a clinical event scale of disease severity (evaluated up to Day 28):
 1. Death
 2. Requiring mechanical ventilation and/or in ICU
 3. non-ICU hospitalization, requiring supplemental oxygen;
 4. non-ICU hospitalization, not requiring supplemental oxygen;
 5. a stay of >24 hours for observation in an ED, field hospital, or other healthcare unit*
 6. any receipt of O2 for >24 hours, outside of hospital*
 7. Not hospitalized, but with clinical and laboratory evidence² of COVID-19 infection

² Positive molecular testing for SARS-CoV-2

*with surge of infections in December 2020 and hospitals becoming more full, these two were put into the clinical events scale as hospitalization equivalents

Other Objectives:

1. Compare the anti-SARS-CoV-2 convalescent plasma and control (SARS-CoV-2 non-immune plasma) groups' anti-SARS-CoV-2 titers at days -1 to 0, 1, 7, 14 and 90.
2. Compare the rates and duration of SARS-CoV-2 molecular testing positivity amongst the anti-SARS-CoV-2 convalescent plasma and control (SARS-CoV-2 non-immune plasma) groups at days 1, 7, 14 and 28
3. Compare the levels of SARS-CoV-2 RNA amongst the anti-SARS-CoV-2 convalescent plasma and control (SARS-CoV-2 non-immune plasma) groups at days -1 to 0, 1, 7, 14 and 28

Table of Contents

1. PROTOCOL SUMMARY:	1
1.1. STUDY POPULATION:	5
1.1.1. Inclusion Criteria for Enrollment:	5
1.1.2. Exclusion Criteria	5
2. LIST OF ABBREVIATIONS:	5
3. BACKGROUND AND SCIENTIFIC RATIONALE	6

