4. INVESTIGATIONAL PLAN

4.1. Study Objectives

4.1.1. Primary Efficacy Objective: Evaluate at day 28, the efficacy of treatment with high-titer Anti- SARS-CoV-2 plasma versus control (SARS-CoV-2 non-immune plasma) in subjects exposed to COVID-19

4.1.2. Primary Safety Objective: Evaluate the safety of treatment with high-titer Anti-SARS-CoV-2 plasma versus control (SARS-CoV-2 non-immune plasma) in subjects exposed to COVID-19

4.1.3. Secondary Objectives:

- I. Cumulative incidence of disease severity between the anti-SARS-CoV-2 convalescent plasma and control groups after individuals develop SARS-CoV-2 infection. Severity of disease will be measured using a clinical event scale of disease severity (evaluated up to Day 28):
 1. Death
 2. Requiring mechanical ventilation and/or in ICU
 3. non-ICU hospitalization, requiring supplemental oxygen;
 4. non-ICU hospitalization, not requiring supplemental oxygen;
 5. Not hospitalized, but with clinical and laboratory evidence³ of COVID-19 infection

4.1.4. Other Objectives:

³ Validated test for presence of SARS-CoV-2

- I. Compare the anti-SARS-CoV-2 convalescent plasma and control (SARS-CoV-2 non-immune plasma) groups for anti-SARS-CoV-2 titers at days -1 to 0, 1, 7, 14 and 90
- II. Compare the rates and duration of SARS-CoV-2 molecular testing positivity amongst the anti-SARS-CoV-2 convalescent plasma and control (SARS-CoV-2 non-immune plasma) groups at days 1, 7, 14 and 28
- III. Compare the levels of SARS-CoV-2 RNA amongst the anti-SARS-CoV-2 convalescent plasma and control (SARS-CoV-2 non-immune plasma) groups at days -1 to 0, 1, 7, 14 and 28
- IV. Understand how the immune system responds to COVID-19 infections and try to understand why some people have mild symptoms and other people have life-threatening disease.

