5.3. Endpoints

Primary Efficacy Endpoint:

28 day incidence of COVID-19 infection with both clinical and laboratory evidence.

Primary Safety Endpoints:

1. Cumulative incidence of serious adverse events categorized separately as either severe infusion reactions and ARDS during the study period
2. Cumulative incidence of grade 3 and 4 adverse events during the study period

Secondary Endpoints

1. 28 day incidence of severe COVID-19 infection defined by death or initiation of mechanical ventilation.
2. Anti-SARS-CoV-2 titers at days -1 to 0, 1, 7, 14, and 90.
3. Rates and duration of SARS-CoV-2 molecular testing positivity at days 1, 7, 14, and 28.

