6.1. EFFICACY, VIROLOGIC AND PK MEASURES

Clinical Efficacy (clinical event scale of disease severity)

- 1 Death
- 2 Requiring mechanical ventilation and/or in ICU
- 3 Non-ICU hospitalization, requiring supplemental oxygen;
- 4 Non-ICU hospitalization, not requiring supplemental oxygen;
- 5 Not hospitalized, but with clinical and laboratory evidence¹⁰ of COVID-19 infection

Virologic measures

1. Rates and duration of SARS-CoV-2 molecular testing positivity at days 1, 7, 14, and 28
2. virological studies of SARS-CoV-2 RNA at days -1 to 0, 1, 7, 14, and 28

Pharmacokinetic (PK) measures: Anti-SARS-CoV-2 titers at days -1 to 0, 1, 7, 14 and 90.

Using samples from 20 donors, we will measure the viral growth inhibition titers of SARS-CoV-2 neutralizing antibodies compared to the current FDA benchmark neutralizing titer of 1:320. However, the ability to detect neutralizing antibodies for SARS-CoV-2 through true viral neutralization in culture is time consuming. Other approaches include in-house ELISA tests for the receptor binding subdomain on the external spike glycoprotein trimer, which correlate with viral culture neutralization in previous coronavirus work. Finally, there are an increasing number of non-FDA validated, commercial ELISA tests with the entire spike

¹⁰ Positive molecular test for SARS-CoV-2

glycoprotein trimer or nucleocapsid as capture proteins. The viral specificity of these commercial ELISA assays for antibodies to the more frequent common cold beta coronavirus like OC43 or the rare SARS-CoV-1 as well as sensitivity for SARS-CoV-2 antibodies is evolving in the ongoing pandemic. Therefore, we will compare the SARS-CoV-2 donor plasma neutralizing titer levels to the whole protein commercial ELISAs being adopted by hospitals versus the receptor binding domain ELISAs. The goal will be to accurately determine the correlation of serum antibody titers measured by the two ELISA assays to virus neutralization titers determined with SARS-CoV-2 live virus.

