## Study Design

CSSC-001 is a two-arm, parallel-group, multi-center, randomized superiority trial in which outpatient adults with recent exposure to SARS-CoV-2 but no current infection will be randomized to receive either human coronavirus immune plasma (HCIP) or control (SARS-CoV-2 non-immune) plasma. This randomized, double-blind, controlled, phase 2 trial will assess the efficacy and safety of HCIP to reduce the cumulative incidence of the development of COVID-19 during study follow-up. Adults 18 years of age or older, with high risk exposure (see below for definition) to person with COVID-19 within 96 hours of enrollment (and 120 hours of receipt of plasma). A total of approximately 500 eligible subjects will be randomized in a 1:1 ratio to either HCIP or control plasma.

**High risk exposure will be defined** as currently defined by CDC and modified as the CDC makes changes. Currently this includes any close contact exposure (as defined by CDC guidelines) to person with COVID-19. Health Care Personnel (HCP) are defined as physicians, nurses, nursing assistants, therapists, technicians, emergency medical service personnel, dental personnel, pharmacists, laboratory personnel, autopsy

personnel, students, trainees and contractual staff. Persons not directly involved in patient care such as clerical, dietary, housekeeping, laundry, security, maintenance, billing, and volunteers, but who are potentially exposed to SARS-CoV-2 in the healthcare setting, also fall under the category of HCP in this protocol.

*Primary Outcome:*

- The primary outcome of CSSC-001 will be the cumulative incidence by day 28 of the development of COVID-19 (symptoms compatible with infection and/or RT-PCR positive) regardless of disease severity comparing those randomized to HCIP to those who are transfused with control plasma.

*Secondary Outcome:*

- Compare the cumulative incidence of disease severity between those randomized to HCIP and control plasma. Severity of disease will be measured using a clinical event scale of disease severity evaluated up to Day 28:
  1. Death
  2. Requiring mechanical ventilation and/or in ICU
  3. non-ICU hospitalization, requiring supplemental oxygen;
  4. non-ICU hospitalization, not requiring supplemental oxygen, or a stay of >24 hours for observation in an ED, field hospital, or other healthcare unit\*, or any receipt of O2 for >24 hours, outside of hospital\*

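### The secondary severity outcome has four definitions in current text, and protocol and SAP also disagree on its population, method and cut-off day

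*Protocol*

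**What the plan says.** - **Protocol summary, Secondary Objectives:** seven levels. Level 5 is "a stay of >24 hours for observation in an ED, field hospital, or other healthcare unit" and level 6 is "any receipt of O2 for >24 hours, outside of hospital". Both sit below non-ICU hospitalization (levels 3 and 4). The scale ends with "7. Not hospitalized, but with clinical and laboratory evidence² of COVID-19 infection". A footnote ties the two additions to the December 2020 surge and describes them as equivalent to hospitalization.
- **Protocol 4.1.3 and 6.1:** five levels, without the two additions. In 4.1.3 the last level is "5. Not hospitalized, but with clinical and laboratory evidence³ of COVID-19 infection". The laboratory footnote differs as well: any validated test in 4.1.3, a positive molecular test in 6.1.
- **Protocol 5.3:** the first secondary endpoint is "28 day incidence of severe COVID-19 infection defined by death or initiation of mechanical ventilation". The ordinal scale is not listed as an endpoint.
- **Protocol 5.2.2:** the severity analysis covers only participants who became infected. It estimates a separate cumulative incidence for each clinical event with the TMLE approach. The objective in the summary and in 4.1.3 is likewise worded as applying after infection.
- **SAP, Study Design and Secondary Analyses:** seven levels, stated the same way in both places. Level 4 is "non-ICU hospitalization, not requiring supplemental oxygen, or a stay of >24 hours for observation in an ED, field hospital, or other healthcare unit", and it goes on to include out-of-hospital oxygen. Level 5 is symptomatic infection, level 6 asymptomatic infection and level 7 no indication of infection.
- **SAP, analysis of the scale:** the Power and Sample Size section applies modified intention-to-treat to all analyses. Secondary Analyses specifies one doubly robust ordinal estimator on status by day 32. Study Design says the scale is evaluated up to Day 28.

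**The concern.** These texts lead to different secondary results from the same data. Only the SAP scale treats the two added events as equivalent to hospitalization; the protocol summary ranks them below it, and the protocol body omits them.

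The population difference matters more. Becoming infected is a post-randomization event that the plasma is meant to change. An analysis restricted to infected participants therefore compares groups that randomization no longer balances. An analysis of everyone transfused keeps the randomized comparison, apart from those excluded before infusion. These are two different estimands under one name. Left unreconciled, a reader of the final report could not tell which secondary result had been planned.

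**Working it through.** The plan states no sample size, power or event count for severity, so there is no figure to reproduce. The check is a comparison of texts, then the size of each analysis set.

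**1. The same participant under each definition**

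| Participant | Summary | 4.1.3 / 6.1 | 5.3 | SAP |
|---|---|---|---|---|
| Death | 1 | 1 | event | 1 |
| ICU, not ventilated | 2 | 2 | no event | 2 |
| Symptomatic, PCR-positive, observed >24 h, not admitted | 5 | 5 (lowest) | no event | 4 |
| Symptomatic, PCR-positive, home oxygen >24 h | 6 | 5 (lowest) | no event | 4 |
| Symptomatic, PCR-positive, at home | 7 | 5 | no event | 5 |
| PCR-positive, no symptoms | none | none | no event | 6 |
| Uninfected, no symptoms | outside analysis | outside analysis | no event | 7 |
| Compatible symptoms, no positive test, not hospitalized | none | none | no event | none |

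**2. Numbering versus substance.** The fifth row is one category under different numbers. Across the three scales, the categories that really change are observation stays, out-of-hospital oxygen, asymptomatic infection and no infection. The last row shows a gap in the SAP scale itself: level 5 needs symptoms and a positive test, level 6 needs a positive test without symptoms, and level 7 needs neither.

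**3. Size of the analysis sets.** Inputs from protocol 5.1: 500 participants, 1:1, with symptomatic disease in 13% of controls and 6.5% of the active arm.
- Control: 250 × 0.13 = 32.5
- Active: 250 × 0.065 = 16.25
- Total: 48.75, or 48.75 / 500 = 9.75%

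Protocol 5.2.2 would therefore analyze about 49 symptomatic cases plus any asymptomatic infections. The SAP would analyze about 500, less those never infused.

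**4. Cut-off day.** The protocol's day 28 visit has a window of 3 days either side, so it closes on day 28 + 3 = 31. The SAP's day 32 matches neither its own Day 28 nor the end of that window.

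**5. Expected events under 5.3.** The documents give no ventilation rate. With r the share of symptomatic cases having the event, the expected count is 48.75 × r, and the chance of no event is (1 − 0.13r)^250 × (1 − 0.065r)^250.

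| r | Source | Expected | Chance of none |
|---|---|---|---|
| 1.4% | protocol 8.3 case fatality (deaths only) | 0.68 | 51% |
| 3.4% | assumption, borrowing the ARDS frequency cited in 8.3 | 1.66 | 19% |
| 10% | assumption | 4.9 | 0.7% |

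The 1.4% is stated in 8.3 alongside 75 per arm and 20% and 5% incidence, so applying it to the 5.1 rates is itself an assumption.

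**The case against.** The best defense is that the SAP governs. It states one scale twice without variation, names its estimator, and is later: it cites a comorbidity list dated 5/29/2021, against a protocol dated December 23, 2020. The five-level versions look like an incomplete update, not a rival plan. This stands as a reason to build on the SAP. It does not settle the matter, because nothing in the text available says that the SAP overrides the protocol. Parts of both documents were not available, so a precedence rule may exist elsewhere.

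The 5.3 composite could also be a separate endpoint alongside the scale. If so, the narrower defect remains: the SAP gives it no analysis, and 5.3 omits the scale.

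Level numbers matter less where each event is analyzed separately, as in 5.2.2. Order still enters there through the rule that interval-censors the lower events a participant skipped.

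The SAP analysis is not ideal either. Up to about 90% of participants (100 − 9.75 = 90.25%) could fall in level 7, so its contrast would largely reflect infected versus uninfected, close to the primary outcome.

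A reader might infer three stronger points that the documents do not support:
- **That the 5.3 endpoint has essentially no power.** Few events are likely, but without a ventilation rate no power figure can be derived.
- **That results were, or will be, chosen after the fact.** The documents contain no results; they only leave room for that choice.
- **That most participants are reclassified.** Part of the mismatch is numbering, and no frequency is given for observation stays or home oxygen.

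**Conclusion.** The inconsistency is real, and it is in current text. There are four definitions of severity, two analysis populations (about 49 symptomatic cases plus any asymptomatic infections, against about 500), two methods and two cut-off days. Following both documents as written cannot give a single secondary severity result.

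The set sizes rest on the planned 13% and 6.5% rates. The 5.3 event counts, about 0.7 to 4.9, rest on the assumed rates shown and illustrate sparsity only. The point concerns a secondary outcome and should be corrected; it does not by itself threaten the primary analysis.

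**What to change.** Before unblinding:

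1. Adopt the SAP 7-level scale, the modified intention-to-treat population of all participants and the ordinal estimator in the protocol summary, 4.1.3, 5.2.2, 5.3 and 6.1.
2. Remove the infected-only restriction from 5.2.2 and the matching wording in the summary and 4.1.3, or label that analysis descriptive. Inserting the SAP scale while keeping the restriction would leave level 7 empty by construction.
3. State one cut-off day and use it in both SAP sections and the protocol.
4. Define a level for participants with compatible symptoms but no positive test, and use one laboratory criterion throughout.
5. List the 5.3 composite as descriptive, or remove it.

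The cost is small but not purely editorial. Neither document shows that observation stays and out-of-hospital oxygen were recorded for participants enrolled before December 2020. That needs checking, and any gap in capture should be stated with the scale.

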6. STUDY PROCEDURES

Day -1 to 0

In-person visit

- A. Screening (must be completed before randomization)
- B. Informed consent (may be obtained prior to Day-1 and before performing study related activities)
- C. Baseline Evaluation (at screening)
 1. Demographics (Age, sex ethnicity, race, number of people in household)
 2. Medical history (timing of exposure to COVID-19 source patient, acute and chronic medical condition, medications, allergies. Any medical condition arising after consent should be recorded as AE)
 3. COVID-19 symptom screen (fevers, cough, shortness of breath)
 4. Vital signs
 6. COVID-19 molecular testing prior to infusion, from nasopharyngeal, throat samples (may be omitted if test already performed on same day as part of usual care)
 7. Draw and result ABO and Rh if no documented ABO typing within the past year.
 8. CBC, comprehensive metabolic panel
 9. Stored samples for future studies

10. Urine or serum pregnancy test for females of childbearing potential. Results from laboratory tests obtained up to 7 days before randomization may be used for the pregnancy test.
11. Determination of eligibility as per inclusion/exclusion criteria
12. Confirmation of emergency contact information in EMR.

To the extent possible and with goal of minimizing exposure of health care workers and study team members to risk, there will be a pre-visit explanation and consent done using a video platform at sites that permit video platform use.

Day 0

In-person visit

1. Randomization of eligible subject in IWRS
2. Study Plasma Administration: A single unit of plasma will be transfused. Time at start and end of infusion will be recorded and Vital signs will be measured immediately prior to infusion, 10-20 minutes after start of infusion, at completion of infusion and 30-60 minutes after the end of the infusion.
3. COVID-19 symptom screen (fevers, cough, shortness of breath). Done by telephone before they come in for transfusion.
4. Assessment of clinical status (composite outcome of disease severity)
5. New medical conditions, concomitant medication, AE evaluation
6. Physical examination

Day 1, (+/-) 1 day

In-person visit

1. Vital signs
2. COVID-19 symptom screen (fevers, cough, shortness of breath)
3. Assessment of clinical status (clinical event scale of disease severity)
4. New medical conditions, AE evaluation
5. CBC, comprehensive metabolic panel
6. COVID-19 molecular testing from nasopharyngeal, throat samples
7. Stored samples for future studies

Day 3, (+/-) 1 day

Phone Call

1. COVID-19 symptom screen (fevers, cough, shortness of breath)
2. Assessment of clinical status (clinical event scale of disease severity)
3. New medical conditions, AE evaluation

Day 7, (+/-) 1 day

In-person visit

1. Vital signs
2. COVID-19 symptom screen (fevers, cough, shortness of breath)
3. Assessment of clinical status (clinical event scale of disease severity)
4. New medical conditions, AE evaluation
5. CBC, comprehensive metabolic panel
6. COVID-19 molecular testing from nasopharyngeal, throat samples
7. Stored samples for future studies

Day 14, (+/-) 3 days

In-person visit

1. Vital signs
2. COVID-19 symptom screen (fevers, cough, shortness of breath)
3. Assessment of clinical status (clinical event scale of disease severity)
4. New medical conditions, AE evaluation
5. CBC, comprehensive metabolic panel
6. COVID-19 molecular testing from nasopharyngeal, throat samples
7. Stored samples for future studies

Day 28, (+/-) 3 days

In-person visit

1. COVID-19 symptom screen (fevers, cough, shortness of breath)
2. Assessment of clinical status (clinical event scale of disease severity)
3. New medical conditions, AE evaluation
4. COVID-19 molecular testing from nasopharyngeal, throat samples

Day 60, (+/-) 3 days

Phone Call

1. COVID-19 symptom screen (fevers, cough, shortness of breath)
2. Assessment of clinical status (clinical event scale of disease severity)
3. New medical conditions, AE evaluation

Day 90, (+/-) 8 days

In-person visit

1. Stored samples for future studies

Clinical research sites for infusion and follow-up

Infusion of plasma will occur after subjects have been determined to be at extremely low risk for having an active COVID-19 infection. Specifically, these subjects will be asymptomatic AND have had a negative validated test for coronavirus in the preceding 24 hours. This plan has been discussed and approved by Johns Hopkins Medicine Health Care Epidemiology and Infection Control (HEIC). Local sites will follow their institutional guidelines regarding location and infection control for COVID-19 related research.

Study staff will wear adequate PPE according to local infection control practices. Local sites will follow their institutional guidelines regarding location and infection control for COVID-19 related research. Samples that require transport will be delivered by courier or a member of the research team and triple packaged for travel (e.g. specimen container, leakproof ziplock bag or other container, outer rigid container with marking such as biohazard symbol, medical specimen or diagnostic specimen).

These tests will be processed at a central investigational laboratory and the results of these tests will not be provided to subjects or their treating physicians in real time. Patients who develop signs and symptoms suggestive of COVID-19 will be referred to standard of care coronavirus testing.

The research team may use remote data collection, which may include use of telemedicine in accordance with the [Guidance for Incorporation of Telemedicine into Research with Human Participants](#) to interview and view the participant. (Relying sites may adhere to their own local policies and guidelines for this remote data collection). For residents at nursing facilities, data that is being routinely collected (e.g. vital signs if being done for clinical care purposes or other clinical or medical record information that is collected for clinical care purposes) may be obtained from the nursing facility with appropriate authorization for release.

The testing and specimen collection will be conducted in accordance with the Johns Hopkins HEIC policies for managing patients and with recent COVID exposure, and protection for study staff (mask, PPE when required) as appropriate. The HEIC protocols are:

https://intranet.insidehopkinsmedicine.org/heic/novel_coronavirus/clinical_resources

https://intranet.insidehopkinsmedicine.org/heic/docs/2019-nCoV_outpatient_guidelines.pdf

https://intranet.insidehopkinsmedicine.org/heic/docs/2019-nCoV_patient_discharge_protocol.pdf

Local sites will follow their institutional guidelines regarding infection control and PPE for COVID-19 related research.

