4.3. Study population

4.3.1. Inclusion Criteria for Enrollment

1. Subjects must be 18 years of age or older
2. Close contact exposure (as defined by CDC guidelines) to person with COVID-19 within 96 hours of randomization (and 120 hours of receipt of plasma)

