Our analysis will be a time to event analysis examining the effect of anti-SARS-CoV-2 plasma. We will estimate the survival function for each treatment arm in order to estimate the risk difference over time as well as the restricted mean survival time which is the area under the survival function and provides the expected mean time to hospitalization or death up to time t^{22} . Our approach will be to estimate the cumulative incidence using the doubly robust estimator based upon targeted minimum loss based estimator as described by Diaz et al [Díaz, I., Colantuoni, E., Hanley, D.F. *et al.* Improved precision in the analysis of randomized trials with survival outcomes, without assuming proportional hazards. *Lifetime Data Anal* **25**, 439–468 (2019)]. By adjusting for baseline covariates that are related to the outcome, we increase precision. The TMLE based approach was shown to increase precision by around 10% to 20% over an inverse probability weighted or augmented inverse probability weighted estimator. As stated above, we will use a hybrid approach of adjusting for pre-specified variables (age) and an algorithmic approach to identify additional variables related to the outcome. Specifically, a random survival forest will be used to identify variables that are related to the outcome in order to increase precision. We will use a random survival forest blinded to the treatment arm allocation and *not* including an indicator variable for treatment. The following pre-randomization variables will be considered: clinical site, race, ethnicity, sex, category of exposure, hematology factors and other laboratory markers (i.e., CBC and metabolic panels), body mass index, ABO blood group, targeted physical exam, and prior comorbidities that have specifically been associated with worse COVID-19 outcomes including: asthma, chronic kidney disease, chronic lung disease (COPD, idiopathic pulmonary fibrosis, cystic fibrosis), diabetes, hemoglobin disorders (thalassemia, sickle cell disease), immunocompromised (cancer, HIV, organ transplantation, prolonged use of corticosteroids), chronic liver disease,

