Analyses will be done to explore differences in the outcomes between the treatment groups. Results of these analyses will be presented unadjusted (crude) and adjusted for covariates. Variables chosen for adjustment are specifically for increasing precision in estimates of treatment efficacy and thus must be predictive of disease outcome [Diaz et al, Lifetime Data Anal (2019): 25]. To identify the adjustment variables, we will utilize a hybrid approach of pre-specifying some variables and using an algorithmic approach to identify variables to adjust for among pre-specified candidate variables. Variables that we are near certain to be predictive of outcome will be adjusted for. Age has been consistently related to worse outcomes for COVID-19 and therefore will be included in analyses for adjustment. Other pre-specified variables that will be candidates for inclusion in primary analysis will be determined via an algorithmic approach and these variables will include: clinical site, race, ethnicity, sex, category of exposure, hematology factors and other laboratory markers (i.e., CBC and metabolic panels), body mass index, ABO blood group, prescription steroid, targeted physical exam, and prior comorbidities that have specifically been associated with worse COVID-19 outcomes including: asthma, chronic kidney disease, chronic lung disease (COPD, idiopathic pulmonary fibrosis, cystic fibrosis), diabetes, hemoglobin disorders (thalassemia, sickle cell disease), immunocompromising conditions (cancer, HIV, organ transplantation, prolonged use of corticosteroids), chronic liver disease, hypertension, and serious heart conditions (heart failure, coronary artery disease, cardiomyopathies, pulmonary hypertension), obesity, smoking status, dementia, down syndrome, pregnancy, stroke/cerebrovascular disease, and substance use disorders [updated to CDC list on website on 5/29/2021 and Guan et al Eur Respir J. 2020 May; 55(5)]. To determine which of these pre-specified candidate variables to be included, we will conduct variable selection by random survival forest in the entire sample (i.e., not including an indicator term for treatment arm) and blinded to treatment allocation. The variable importance and 95% confidence intervals [Ishwaran et al Statistics in Medicine. 2019;38] shall be used to identify predictive variables for the outcome and included in analytical models. Specifically, variables in which the 95% CI for the variable importance from the random forest does not contain 0 will be adjusted for. This should reduce the number of variables that the analysis adjusts for in order to minimize the degrees of freedom that are used while allowing the analysis to include the variables that have the most correlation with the outcome in order to maximize precision. This hybrid approach will be done on the full sample (i.e., modified ITT sample) and not include the treatment arm (i.e., among entire sample without controlling for convalescent or control plasma) in order to identify the prognostic baseline variables for entire sample.

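### The candidate covariates omit exposure timing and household size, both recorded before randomisation, and include a physical examination that is scheduled only at the Day 0 transfusion visit

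*Protocol*

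**What the plan says.** **What is collected before randomisation.** Protocol section 6, Day -1 to 0, opens with "Screening (must be completed before randomization". Its demographics item includes the number of people in the household, and its medical history item includes "timing of exposure to COVID-19 source patient". Entry requires an exposure "within 96 hours of randomization (and 120 hours of receipt of plasma" (Protocol 4.3.1), so time since exposure varies between participants.

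**What may be adjusted for.** Age is always included. Other covariates come from a candidate list screened by a random survival forest that ignores treatment arm. Protocol 5.2 starts the list: "The following pre-randomization variables will be considered: clinical site, race, ethnicity, sex, category of exposure, hematology factors and other laboratory markers". It continues with "body mass index, ABO blood group, targeted physical exam, and prior comorbidities" linked to worse COVID-19 outcomes. The SAP (Statistical Principles) has a slightly longer list containing "prescription steroid, targeted physical exam, and prior comorbidities". The SAP twice more calls these variables pre-randomisation, at the end of the covariate discussion and in Primary Analysis.

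**When the physical examination takes place.** In the Schedule of Events (under Protocol 4.3.2) its single mark is in the Transfusion column, while Randomization is marked in the Baseline column. In section 6 it is item 6 of the Day 0 list, whose item 1 is "Randomization of eligible subject in IWRS". The screening visit has vital signs but no physical examination.

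**The concern.** Covariate adjustment helps here only through variables that predict the primary outcome. The SAP's working definition of that outcome is a positive molecular test with or without symptoms. The comorbidity candidates were chosen because they predict a bad course of disease, and the SAP gives the same reason for including age. Predicting severity and predicting acquisition are different aims.

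Two baseline items that plausibly bear on acquisition are recorded but cannot enter the model. Participants must have a negative molecular test within 24 hours before infusion (Protocol 4.3.4). Someone still negative late in the 96-hour window plausibly has a different remaining risk from someone negative soon after exposure. Household size plausibly relates to continuing exposure. At stake is some precision, not validity.

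The examination is a separate matter. A covariate measured after treatment starts can itself be affected by treatment, which is why the plan limits candidates to pre-randomisation variables. The plan names one candidate for which it schedules no pre-randomisation measurement.

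**Working it through.** **1. Lists against schedule**

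| Item | When recorded | Candidate covariate? |
|---|---|---|
| Timing of exposure | Screening | No, in either document |
| People in household | Screening | No, in either document |
| Category of exposure | Not defined as a covariate | Yes, in both; timing not mentioned |
| Physical examination | Day 0, Transfusion column only | Yes, in both, under a pre-randomisation label |

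The numbered screening list jumps from item 4 to item 6, so an examination may once have stood there. The Schedule of Events also shows none at screening.

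**2. The plan's own sample size (background)**

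Inputs: control risk 0.13, active risk 0.065, one-sided alpha 0.05, power 0.80 (Protocol 5.1; SAP, Power and Sample Size).

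- Hazard ratio under an exponential model: ln(0.935)/ln(0.87) = 0.4826, so |ln HR| = 0.7286.
- Events (Schoenfeld): 4 × (1.645 + 0.842)² / 0.7286² = 46.6.
- Mean risk: (0.13 + 0.065)/2 = 0.0975. Total: 46.6/0.0975 = 478, against the stated 488. That is 2% apart, close enough to use as a base.

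**3. How much outcome variance timing could explain**

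The documents do not say how prognostic timing is, so I assume a range. Let t be hours/96, uniform on 0 to 1, with logit p(t) linear in t, odds changing by a factor OR across the window, and mean risk 0.0975. Then R² = Var(p) / (0.0975 × 0.9025) = Var(p)/0.0880.

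**4. What that does to power at 500**

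Expected events: 500 × 0.0975 = 48.75. If adjustment cuts the variance by R²:

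power = Φ( √(48.75 / [4(1 − R²)]) × 0.7286 − 1.645 )

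With R² = 0: √12.19 × 0.7286 = 2.543, and Φ(0.899) = 81.6%.

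| OR across 0–96 h (assumed) | Risks at the two ends | Var(p) | R² | Power | 500 × R² |
|---|---|---|---|---|---|
| none | 9.75% throughout | 0 | 0 | 81.6% | 0 |
| 2 | 13.1%, 7.0% | 0.00031 | 0.35% | 81.7% | about 2 participants |
| 3 | 15.2%, 5.7% | 0.00076 | 0.86% | 81.8% | about 4 |
| 5 | 18.2%, 4.2% | 0.00159 | 1.81% | 82.2% | about 9 |

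Applying R² to an event-count formula is an approximation, good enough for the order of magnitude.

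**5. Would the variable be selected?**

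A candidate is adjusted for only if the 95% interval for its forest importance excludes zero. As a rough stand-in, a two-sided 5% Wald test in a logistic model with about 49 events detects timing with probability of about 26% at OR 2, just over 50% at OR 3 and over 80% at OR 5. At the weak end it would usually not be selected.

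No comparable figure can be given for household size or for the physical examination.

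**The case against.** The strongest reply is that the first half is a preference. Neither document promises to list every variable collected, and the choice of candidates belongs to the trialists. The list is not blind to acquisition, since it has clinical site and category of exposure. Leaving out a prognostic covariate does not bias a randomised comparison. The gain is tiny, rests on assumed odds ratios and may not appear at all, because the forest may not select the variable. The SAP also limits adjusters deliberately to save degrees of freedom. All of this stands. It makes the change optional and rules out calling it costless. It does not explain why two recorded, plausible predictors of the endpoint are missing from a list meant to contain such predictors.

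On the examination, a reader might infer from the Day 0 list that it takes place after plasma is given. The documents do not support that. The list is not chronological: item 3, the symptom screen, is done by telephone before the participant comes in, yet follows item 2, plasma administration. The Transfusion column identifies the visit, not the order within it, and both columns fall on Day 0.

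It can also be said that the label "The following pre-randomization variables will be considered" already excludes later findings. That is a fair reading, but it leaves a named candidate with no scheduled pre-randomisation source, so an analyst still has to guess what to use.

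**Conclusion.** Two small points stand.

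First, timing of exposure and household size are recorded before randomisation, plausibly predict infection, and are not candidates. The cost is lost precision worth at most about 0.6 percentage points of power for timing (81.6% to 82.2%). This assumes odds that change 2- to 5-fold across the window, exposure times spread evenly over it, and a variable that is selected or forced in. A reader might infer that the treatment estimate is biased or the trial underpowered as a result; neither follows.

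Second, the pre-randomisation label and the physical examination schedule do not match and should be reconciled. If the examination precedes the infusion, masking makes any bias negligible. If it follows, findings could reflect an infusion reaction. The documents do not settle which, so they do not show that a treatment-affected covariate would be used. The practical effect is probably negligible.

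This is an optional improvement plus a clarification. Neither threatens the primary analysis.

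**What to change.** Before unblinding, and preferably before the selection forest is run:

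- Add hours from exposure to randomisation and number of people in the household to the candidate list in Protocol 5.2 and SAP Statistical Principles. If the team wants the gain from timing regardless of the selection step, it can be forced in alongside age.
- Say what category of exposure contains.
- Drop the targeted physical examination as a covariate, or restrict it to findings recorded before randomisation and name their source.

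The cost is a few lines of SAP text and no new data collection. The downside is two more candidates in the selection step and possibly one or two more adjustment terms, with about 49 events expected.
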